13.6 Day 60 Visit

At the day 60 visit assessment includes, by telephone from the LTCH or by in person visit:

- SAEs, hospitalizations, deaths for residents
- Number of microbiologically confirmed COVID-19 cases that have been identified in staff and residents to day 60.

13.7 Early Termination Visit

If a participant chooses to withdraw from the study prematurely after the baseline visit but **before day 40**, efforts will be made to complete all study activities required at the day 40 visit. Participants who discontinue study drug prematurely but consent to still be followed up in the study should follow routine protocol-defined procedures.

14. EVALUATION, RECORD, AND REPORTING OF ADVERSE EVENTS

14.1 Definitions

14.1.1 Adverse Event (AE)

An AE is any untoward medical occurrence in a patient or clinical investigation participant, administered a study medication/intervention, which does not necessarily have a causal relationship with this treatment. An AE can therefore be any unfavorable and unintended sign (including an abnormal laboratory finding), symptom, or disease temporally associated with the use of a medicinal (investigational) study medication/intervention, whether or not related to the medicinal (investigational) study medication/intervention.

During each follow-up visit with the participant, information on AEs will be gathered and documented accordingly. AEs will be graded as mild, moderate, severe or life-threatening and assessed by causality as probably related, possibly related, unlikely to be related or not related to the study drug (investigational arm only).

Stable chronic conditions which are present prior to clinical trial entry and do not worsen are not considered AEs and will be accounted for in the participant's medical history.

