9.2 Blinding

The trial will be blinded with the use of placebo controls. Favipiravir will have a placebo which is similar in size and shape, but can be distinguished because of color differences and an imprint on the surface of favipiravir tablets which could not be matched for the placebo given the timelines of this trial. However, favipiravir and placebo will be packaged in blister packages of identical appearance.

Drug supply will be dispensed by external pharmacies, which supply multiple LTCHs, therefore we will not be able to completely rule out that pharmacists dispensing medication will remain blinded. In addition, both placebo and favipiravir can be crushed before administration, which is necessary for some residents, and will not be identical in appearance when crushed. However, since favipiravir is not otherwise available in Canada, residents of included LTCHs will only receive one type of intervention (either drug or placebo, depending on the allocation of the LTCH unit), and no information will be provided by external pharmacies, research personnel or investigators to the LTCHs about, color, imprinting, appearance after crushing, and about the allocated intervention. Therefore, it is unlikely that LTCH staff and residents will be unblinded.

All study investigators will be blinded, except for an independent statistician from AHRC who will be responsible for probabilistic minimization, but will otherwise not be involved in the conduct of the trial. Outcome assessors, who will extract outcome data from the LTCHs' administrative data, will be blind to treatment allocation. The statistician conducting the analysis will also be unaware of treatment allocation.

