9.3 Emergency unblinding

Code breaks should occur only in exceptional circumstances when knowledge of the actual treatment is absolutely essential for further management of the patient. The resident's attending physician and/or the LTCH Medical Director or Directors of Nursing are encouraged to discuss with the Principal Investigator if they believe that unblinding is necessary. If unblinding is considered necessary, the Principal Investigator will contact the independent statistician at the AHRC, who will do the code break as deemed necessary and communicate it directly to resident's attending physician. Similarly, a staff member's family or attending physician will be encouraged to consult with the Principal Investigator the need to unblind for LTCH staff.

Medical directors, investigators and research personnel are encouraged to maintain the blind as far as possible. The actual allocation must not be disclosed to LTCH staff or patients and/or other research personnel, investigators or sponsors. In addition, there should not be any disclosure of the code in any of the corresponding patient documents. Medical director and Principal Investigator must report all code breaks with reason as they occur on the corresponding CRF page. Unblinding should not necessarily be a reason for study drug discontinuation.

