10.1.3 Formulation and Packaging

Favipiravir will be provided to the study team from the manufacturer (Avigan®; FUJIFILM Toyama Chemical Co., Ltd) via Appili Therapeutics. The medication is supplied as tablets and is orally administered. Appili will supply placebo tablets of similar but not identical appearance, with a formulation equivalent to the active product, minus the active pharmaceutical ingredient.

Favipiravir can be crushed for persons unable to swallow tablets. If necessary, nurses at the bedside will crush favipiravir or placebo tablets immediately before administration and disperse them in water, cranberry juice or apple sauce for administration to residents either orally or by feeding tube (for residents who have pre-existing chronic feeding tubes) who cannot swallow tablets.

Details of the chemical composition and appearance are provided below in Table 1. Favipiravir will be provided in blister packs. All study products (Favipiravir and placebo) will be labeled as Investigational Product in accordance with Health Canada regulations.

Table 1. Formulation, Appearance and Composition of Favipiravir®

	Avigan®		
	Tablet		
Formulation	C5H4FN3O2; favipiravir		
DIN			
Appearance	Light yellow round tablet 8.7 mm in		
	diameter		
Non-	Colloidal silicon dioxide (diluent),		
medicinal	povidone K30 (binder), low-		
ingredients	substituted hydroxypropyl cellulose		
	(disintegrant), crospovidone		
	(disintegrant), and sodium stearyl		
	fumarate (lubricant). Film coated with		
	OPADRY, which includes		
	Hypromellose (2910, 6mPas), titanium		
	dioxide, talc, and yellow ferric oxide.		

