14.2 AE Descriptions and Recording

Grading of AEs will be done by study staff and investigators according to the Division of AIDS (DAIDS) Table for Grading the Severity of Adult and Pediatric Adverse Events

For all collected AEs (including SAEs), study investigators will also determine the AE's causality based on temporal relationship and his/her clinical judgment. The degree of certainty about causality will be graded using the categories below:

Definitely Related: There is clear evidence to suggest a causal relationship, and other possible contributing factors can be ruled out. The clinical event, including an abnormal laboratory test result, occurs in a plausible time relationship to Investigational Product administration and cannot be explained by concurrent disease or other products or chemicals. The response to withdrawal of the product (de-challenge) should be clinically plausible. The event must be pharmacologically or phenomenologically definitive, with use of a satisfactory re-challenge procedure if necessary.

Probably Related: There is evidence to suggest a causal relationship, and the influence of other factors is unlikely. The clinical event, including an abnormal laboratory test result, occurs within a reasonable time sequence to administration of the Investigational Product, is unlikely to be attributed to concurrent disease or other products or chemicals, and follows a clinically reasonable response on withdrawal (de-challenge). Re-challenge information is not required to fulfill this definition.

Possibly Related: There is some evidence to suggest a causal relationship (e.g., the event occurred within a reasonable time after administration of the trial medication). However, the influence of other factors may have contributed to the event (e.g., the participant's clinical condition, other concomitant events). Although an adverse drug event may rate only as "possibly related" soon after discovery, it can be flagged as requiring more information and later be upgraded to "probably related" or "definitely related", as appropriate.

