Unlikely: A clinical event, including an abnormal laboratory test result, whose temporal relationship to Investigational Product administration makes a causal relationship improbable (e.g., the event did not occur within a reasonable time after administration of the trial medication) and in which other products or chemicals or underlying disease provides plausible explanations (e.g., the participant's clinical condition, other concomitant treatments).

Not related: The AE is completely independent of Investigational Product administration, and/or evidence exists that the event is definitely related to another etiology. There must be an alternative, definitive etiology documented by the clinician.

All SAEs which occur during the course of the study must be reported to the Project Manager within 24 hours of the site becoming aware of the event. The Project Manager will be responsible for reporting SAEs to Health Canada on behalf of the Sponsor. SAEs will be reported to:

Project Manager: [name], CCRP, PMP

[contact] [name]

[contact]

E-mail: [contact]

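### Section 14.1.1 limits adverse-event causality grading to the investigational arm on four grades; this contradicts Section 14.2 (all AEs, five grades) and does not fit the investigator blinding in 9.2 and 9.3

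*Protocol*

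**What the plan says.** Section 14.1.1 describes how adverse events (AEs) are gathered at each follow-up visit, graded for severity and "assessed by causality as probably related, possibly related, unlikely to be related or not related to the study drug (investigational arm only"). That is four grades, with a limit to one arm.

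Section 14.2 returns to causality: "For all collected AEs (including SAEs), study investigators will also determine" it, from the timing of the event and their clinical judgment. It then defines five grades, from definitely related down to not related. The definition of possibly related expects movement up the scale, since "it can be flagged as requiring more information and later be upgraded to" probably or definitely related. The fifth grade, not related, is defined thus: "The AE is completely independent of Investigational Product administration, and/or evidence exists that the event is definitely related to another etiology".

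On who knows the arm, Section 9.2 states: "All study investigators will be blinded, except for an independent statistician from AHRC". That statistician runs the minimization and has no other part in the conduct of the trial. Section 9.3 adds: "Code breaks should occur only in exceptional circumstances when knowledge of the actual treatment is absolutely essential for further management of the patient". A code break is passed directly to the attending physician, and the allocation is not to be disclosed to investigators, other research personnel or the sponsor. Section 13.3 Medical Oversight gives the classification of relatedness to the qualified or principal investigator or a delegated physician, and mentions no arm.

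**The concern.** The protocol fixes one data item twice, in two ways that cannot both be right. Under 14.1.1, an AE on placebo gets no causality grade, and no AE can be graded definitely related. Under 14.2, every AE gets a grade and definitely related is available.

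The first version is also the weaker one for a placebo-controlled trial. A relatedness grade helps a comparison when it is given blind and in both arms, because the placebo arm shows how often assessors attribute background illness to the tablets. In frail care-home residents that background will be substantial. With grades in one arm only, the comparison is lost.

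There is a secondary risk to the blind. Section 9.2 says that "residents of included LTCHs will only receive one type of intervention (either drug or placebo, depending on the allocation of the LTCH unit"). If grades were entered during the trial for one arm only, the presence or absence of a grade for one resident would signal the allocation of that resident's whole unit.

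**Working it through.** No figure in the protocol depends on this point, so the check is a comparison of sections and a count of grades.

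| | Section 14.1.1 | Section 14.2 |
|---|---|---|
| Which AEs | investigational arm only | all collected AEs, SAEs included |
| Definitely related | absent | present |
| Probably related | present | present |
| Possibly related | present | present |
| Unlikely | present | present |
| Not related | present | present |
| Number of grades | 4 | 5 |

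**Scale.** 5 − 4 = 1 grade is missing from 14.1.1. It is a working part of 14.2, which names it as a level to which a possibly related event may later be moved. A form built on 14.1.1 could not record that change.

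**Scope.** Section 14.2 applies to all collected AEs. Section 14.3 says which AEs are collected: any that occur between randomization and a participant's departure from the study, with no distinction by arm. Placebo AEs are therefore collected, and 14.2 asks for a causality grade on them. Section 14.1.1 excludes them. The scope conflict follows from these sections alone.

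**Fit with the blinding.**

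1. The graders are study investigators (14.2), with sign-off by the qualified or principal investigator or a delegated physician (13.3 Medical Oversight).
2. Investigators are blinded (9.2). The one person who holds the allocation has no role in AE assessment.
3. Code breaks serve the management of a patient, and the result goes to the attending physician (9.3). Causality grading is not a listed reason for one.
4. No section names an unblinded causality assessor.

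The graders therefore do not know the arm when they grade and cannot leave placebo events out at that time. The limit could be applied later, when the data are unblinded and tabulated, but 14.1.1 words it as part of the assessment and mentions no later step.

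**Reach.** Section 15.3.2 lists as safety outcomes the number of serious AEs and the proportions whose study medication is stopped because of AEs. Neither uses the four- or five-grade scale. The primary outcome (15.3.1) is outbreak control at unit level, and the sample size (15.2) rests on that alone.

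**The case against.** The best defence is that 14.2 is the operative section. It names the graders, gives the basis for grading and defines each grade, whereas 14.1.1 stands under a heading for definitions and gives a bare list. A careful form-builder would follow 14.2. That is probably what would happen, and it is why the point is minor. It does not make 14.1.1 correct.

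A second defence is that the parenthesis only explains the words before it: a causal link to favipiravir can exist only in the favipiravir arm. The protocol's terms do not settle this. Section 9.1 uses study medication for both products, while the synopsis sets study drug against placebo in its statistical analysis row. Even on this reading, the four grades still conflict with the five.

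A reader might infer three stronger things that the documents do not support.

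- *That the limit cannot be carried out, or forces unblinding.* It does not. Blinded investigators could grade every AE under 14.2, and only the favipiravir grades could be shown after unblinding. Section 14.1.1 does not tell an assessor to learn the allocation. The supportable claim is that the limit cannot be applied at the time of assessment and that no later step is described.
- *That Section 10.1.3 proves 14.2 covers placebo.* It says: "All study products (Favipiravir and placebo) will be labeled as Investigational Product in accordance with Health Canada regulations". This is a labelling statement, and the synopsis describes the investigational product as favipiravir tablets, with placebo in a separate row. The scope conflict rests on 14.2 applying to all collected AEs, without this step.
- *That half the units would lose their grades.* The control arm is 8 of 16 units, but that share applies only if the limit is followed literally, which is the less likely course. It is not an effect size.

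**Conclusion.** Section 14.1.1 is wrong as written, and the point is minor. It contradicts 14.2 on scope (one arm against all collected AEs) and on scale (four grades against five), and its arm limit does not fit graders who are blinded under 9.2 and 9.3.

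No effect on any planned estimate is claimed. Nothing in Section 15 uses the causality grade. The loss of placebo relatedness grades, and with it of a blinded comparison of related AEs, would occur only if the limit in 14.1.1 were followed in place of 14.2.

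The conclusion assumes that the parenthesis is meant as a limit on assessment, which is its plain sense. The mismatch in the number of grades does not need that assumption. The trial is called partially blinded in 6.1, and 9.2 admits that the tablets differ in colour and imprint. Neither statement gives the causality graders planned knowledge of the arm.

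**What to change.** In Section 14.1.1, delete the parenthesis that limits causality assessment to the investigational arm, and replace the list of four grades with a reference to the five-grade scale in 14.2. State there that the scale is applied blind to every AE in both arms.

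The cost is one deleted phrase and one cross-reference. No new data are needed, because 14.2 already asks for a grade on every collected AE. If the case report form was built from 14.1.1, it needs one more response option. Amendments go to the ethics committee under 17.1.1, so the change can be made with the next one.

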14.1.2 Serious Adverse Events (SAEs)

A SAE is defined as an AE meeting one of the following criteria at any dose:

- Results in death during the period of protocol-defined surveillance
- Is a life-threatening event (defined as a participant at immediate risk of death at the time of the event)
- Results in in-patient hospitalization or prolongation of existing hospitalization during the period of protocol-defined surveillance
- Results in persistent or significant disability or incapacity (disability is defined as a substantial disruption of a person's ability to conduct normal life functions)
- Is a congenital anomaly or birth defect

Any other important medical event that may not result in one of the above outcomes, may be considered a SAE when, based upon appropriate medical judgment, the event may jeopardize the participant and may require medical or surgical intervention to prevent one of the outcomes listed above. Examples of such medical events include allergic bronchospasm requiring intensive treatment in an emergency room or at home, blood dyscrasias or convulsions that do not result in in-patient hospitalization, or the development of drug dependency or drug abuse.

Participants will be monitored during the 60-day study period for SAEs. If an SAE is ongoing at the time a participant discontinues/completes the study, the SAE will be followed until the Investigator agrees that the event is satisfactorily resolved, becomes chronic, or that no further follow-up is required.

14.2 AE Descriptions and Recording

Grading of AEs will be done by study staff and investigators according to the Division of AIDS (DAIDS) Table for Grading the Severity of Adult and Pediatric Adverse Events

For all collected AEs (including SAEs), study investigators will also determine the AE's causality based on temporal relationship and his/her clinical judgment. The degree of certainty about causality will be graded using the categories below:

Definitely Related: There is clear evidence to suggest a causal relationship, and other possible contributing factors can be ruled out. The clinical event, including an abnormal laboratory test result, occurs in a plausible time relationship to Investigational Product administration and cannot be explained by concurrent disease or other products or chemicals. The response to withdrawal of the product (de-challenge) should be clinically plausible. The event must be pharmacologically or phenomenologically definitive, with use of a satisfactory re-challenge procedure if necessary.

Probably Related: There is evidence to suggest a causal relationship, and the influence of other factors is unlikely. The clinical event, including an abnormal laboratory test result, occurs within a reasonable time sequence to administration of the Investigational Product, is unlikely to be attributed to concurrent disease or other products or chemicals, and follows a clinically reasonable response on withdrawal (de-challenge). Re-challenge information is not required to fulfill this definition.

Possibly Related: There is some evidence to suggest a causal relationship (e.g., the event occurred within a reasonable time after administration of the trial medication). However, the influence of other factors may have contributed to the event (e.g., the participant's clinical condition, other concomitant events). Although an adverse drug event may rate only as "possibly related" soon after discovery, it can be flagged as requiring more information and later be upgraded to "probably related" or "definitely related", as appropriate.

Unlikely: A clinical event, including an abnormal laboratory test result, whose temporal relationship to Investigational Product administration makes a causal relationship improbable (e.g., the event did not occur within a reasonable time after administration of the trial medication) and in which other products or chemicals or underlying disease provides plausible explanations (e.g., the participant's clinical condition, other concomitant treatments).

Not related: The AE is completely independent of Investigational Product administration, and/or evidence exists that the event is definitely related to another etiology. There must be an alternative, definitive etiology documented by the clinician.

All SAEs which occur during the course of the study must be reported to the Project Manager within 24 hours of the site becoming aware of the event. The Project Manager will be responsible for reporting SAEs to Health Canada on behalf of the Sponsor. SAEs will be reported to:

Project Manager: [name], CCRP, PMP

[contact] [name]

[contact]

E-mail: [contact]

14.3 Follow-up for Adverse Events

Any AE that occurs between the time that a study participant is randomized and the time that s/he departs the study at the end of the final study visit (or at the time of early discontinuation of the participant from the study for any reason) will be captured and recorded.

At each contact with the participant, the investigator (or designate) must seek information on AEs by specific questioning.

All AEs (including SAEs) will be followed until resolution or until the investigator and the clinical/medical monitor are in agreement that the AE has resolved, stabilized or become chronic and no further follow-up is required.

14.4 Pregnancy Follow-up

If a participant becomes pregnant during the study, the Sponsor will collect follow-up data regarding the pregnancy, birth, and status of the child. Follow-up should be continued until study close-out at the study centre. Pregnancy is not an adverse event; however, any complication related to pregnancy should be considered an adverse event. Refer to Section 0.1 to 14.3.

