3. PROTOCOL SYNOPSIS

Full Title	Control of COVID-19 outbreaks in long term care		
Short Title	CONTROL-COVID-1		
Protocol Number	CONTROL-COVID-Favipiravir-1		
Version Number and Date	Version 2.0, June 4, 2020		
Study Duration	Enrollment period: May 10, 2020 to Oct 31, 2020		
	Study period: April 1, 2020 to March 31, 2021		
Principal Investigator	[name]		
Number of Centers	60 screened, 16 enrolled		
Number of participants	Estimated: 760		
Study Design	Placebo-controlled cluster-randomized trial		
Primary Objective	Evaluate the efficacy of favipiravir chemoprophylaxis for control of outbreaks of COVID-19 in long-term care homes (LTCH).		
Secondary Objectives	To compare the following secondary outcomes between study arms:		
	1. The proportion of residents of included LTCH units who die up to day 40, and up to day 60		
	2. The proportion of residents of included LTCH units who were uninfected at baseline and develop new symptomatic microbiologically confirmed COVID-19 up to day 40		
	3. The proportion of exposed staff uninfected at baseline in whom SARS-CoV-2 infection is identified up to day		

	14 and up to day 40		
	4. The proportion of residents of included LTCH units hospitalized up to day 40		
	5. The proportion of residents of included LTCH units who discontinue study medication due to adverse events		
	6. The proportion of LTCH staff of included LTCH units who discontinue study medication due to adverse events.		
	7. The occurrence of new microbiologically confirmed COVID-19 infections in residents in other units of the facility up to day 40 (dichotomous, at LTCH level)		
	8. The proportion of previously unaffected LTCH units of the remainder of the facility in which a case of COVID-19 is identified		
	9. The proportion of residents in the remainder of the facility who develop COVID-19 infections up to day 40		
Sample Size	8 units per arm (16 units in total)		
Randomization	Cluster trial with probabilistic minimization		
Study Population	Residents and staff of LTCH for older adults, Ontario		
Investigational Product Description	Favipiravir 200 mg tablets		
Control	Placebo		
Administration and Dosing	Favipiravir 1600 mg orally twice daily on day one then 800 mg orally twice daily for prophylaxis, and 2000 mg orally twice daily on day one then 1000 mg orally twice daily for treatment		

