7.2.2 Exclusion criteria for LTCH Residents and Staff

- 1. Pregnancy (females < 55 years of age require a negative urine pregnancy test at enrollment, and either menopause or two concurrent reliable methods of contraception need to be confirmed)
- 2. History of abnormalities of uric acid metabolism, other than gout.
- 3. History of hypersensitivity to remdesivir or favipiravir
- 4. Previous diagnosis of hepatic cirrhosis
- 5. Current use of the following medications, which cannot be discontinued for the duration of the study: pyrazinamide, hydralazine, more than 3000 mg of acetaminophen per day

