10. STUDY INTERVENTIONS

10.1 Favipiravir

The study intervention is a 25-day course of favipiravir/placebo for LTCH residents and staff, to be initiated immediately after recognition of the LTCH outbreak.

Favipiravir was approved for novel influenza strains unresponsive to standard antiviral therapies in Japan in 2004, under the trade name Avigan®. It is manufactured by Fujifilm Toyama Chemical Co., Ltd. Favipiravir is a purine nucleoside analogue, which acts as a competitive inhibitor of RNA-dependant RNA polymerase. It has in-vitro activity against influenza A and B including activity against amantadine-, oseltamivir-, and zanamivir-resistant influenza viruses, and several agents of viral hemorrhagic fever, and SARS-CoV-2 *in vitro*. A1-43,71

The duration of prophylaxis was defined to align with the sum of the periods of infectivity and incubation. The average incubation period ranges between 4-6.4 days (ranging from 0-14 days), ^{5,23,75,76} with a 95th percentile of 12.5 days. Further, preliminary literature from Germany suggests that the duration of infectivity is 7-10 days from the onset of symptoms. Prophylaxis will continue until day 25.

New staff starting to work on the unit after day 1 who consent to receiving study drug will continue the drug until day 25 of the outbreak.

Residents in the LTCH unit diagnosed with COVID-19 at enrollment will be offered treatment with study drug for 14 days.

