10.1.2 Dosing in special populations

Favipiravir is contraindicated in nursing mothers and pregnant women or women of child-bearing age who are not taking oral contraception due to its potential teratogenicity.

No alteration of dosing is needed in subjects with renal impairment. Total exposure for plasma favipiravir for subjects with severe renal impairment (Stage 4) was 1.3-fold higher compared to subjects with normal renal function. No obvious effect of renal impairment on safety was observed and favipiravir treatment was generally well tolerated in subjects with renal impairment.

No alterations in dosing strategies are required in older adults. The maximum plasma concentration and AUC values in elderly subjects in a single and a multiple-dose study completed in Japan were higher than in young subjects. Comparing AUC values on Day 5, the differences were 40 and 80% after 600 mg once a day and 400 mg BID, respectively. In the companion study completed in the United States of America, there were no differences between young and older populations based on Day 5 AUC comparison in subjects receiving either 600 or 800 mg BID.

Higher drug levels occur in patients with hepatic impairment, and we have excluded patients with cirrhosis.

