11. RISK MANAGEMENT

11.1 Pregnancy

Favipiravir is contraindicated in pregnancy. If a participant becomes pregnant during the study, the Investigator must inform the Sponsor and the study drug will be discontinued. Follow-

up should be continued until study close-out at the study centre. Pregnancy is not an adverse event; however, any complication related to pregnancy should be considered an adverse event.

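### Pregnancy follow-up is required only until study close-out, which under the stated dates would precede most term births from on-study conceptions, so it does not secure the promised birth and child data

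*Protocol*

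**What the plan says.** Section 14.4 states that if a participant becomes pregnant, "the Sponsor will collect follow-up data regarding the pregnancy, birth, and status of the child". The next sentence sets the duration: "Follow-up should be continued until study close-out at the study centre". Section 11.1 carries the same end point, after the instruction "If a participant becomes pregnant during the study, the Investigator must inform the Sponsor and the study drug will be discontinued". Both sections add that pregnancy is not itself an adverse event, although a complication of it is.

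The protocol does not date close-out. The only calendar dates are in the synopsis: "Enrollment period: May 10, 2020 to Oct 31, 2020" and "Study period: April 1, 2020 to March 31, 2021".

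On exposure, section 10.1 says "The study intervention is a 25-day course of favipiravir/placebo for LTCH residents and staff". Section 10.1.2 names among those for whom the drug is contraindicated "women of child-bearing age who are not taking oral contraception due to its potential teratogenicity". At entry, section 7.2.2 says that "females < 55 years of age require a negative urine pregnancy test at enrollment", together with menopause or two concurrent reliable methods of contraception.

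**The concern.** The two sentences in 14.4 pull against each other. One promises an outcome that arrives about nine months after conception. The other requires follow-up only to an administrative milestone. Because a negative test is required at entry, a pregnancy in this trial will normally be new, or very early, at enrolment. Enrolment may continue until five months before the study period ends, so the milestone can easily come before the birth.

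What is at stake is safety reporting. The protocol itself cites embryo-fetal toxicity findings (section 4.3) and potential teratogenicity (section 10.1.2). The remark in section 8.1 that pregnancy is extremely unlikely rests on the age of the residents, but staff of working age also take the study drug. If a staff member conceives during dosing, the birth outcome is the most informative observation, and the written duty to follow her may have lapsed by then.

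**Working it through.** The protocol gives no figure to reproduce here. The check is calendar arithmetic, followed by a reading of the other follow-up rules.

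**Inputs from the protocol**
- Enrolment period: 10 May to 31 October 2020 (synopsis). Counted inclusively: 22 + 30 + 31 + 31 + 30 + 31 = 175 days.
- End of study period: 31 March 2021 (synopsis), 151 days after the last enrolment day.
- Course of study drug: 25 days (section 10.1), so the last drug day is enrolment plus 24 days.

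**Assumptions not in the protocol**
- Close-out falls on 31 March 2021.
- Conception to birth takes 266 days (term) or 245 days (37 weeks).
- Each enrolment day is treated as a possible study day 1.

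**Formula**
- Birth date = enrolment date + offset of conception + days from conception to birth.
- Last enrolment date with birth by close-out = 31 March 2021 − offset − days to birth.
- Enrolment days after that date, divided by 175, give the share not covered.

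**Results**

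| Conception | Days to birth | Last enrolment date covered | Days not covered | Share |
|---|---|---|---|---|
| At enrolment (offset 0) | 245 | 29 July 2020 | 2 + 31 + 30 + 31 = 94 | 54% |
| At enrolment (offset 0) | 266 | 8 July 2020 | 23 + 31 + 30 + 31 = 115 | 66% |
| Study day 25 (offset 24) | 245 | 5 July 2020 | 26 + 31 + 30 + 31 = 118 | 67% |
| Study day 25 (offset 24) | 266 | 14 June 2020 | 16 + 31 + 31 + 30 + 31 = 139 | 79% |

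A conception on 31 October 2020 gives a birth 245 − 151 = 94 to 266 − 151 = 115 days after 31 March 2021, that is, about 3 to 24 July 2021. A term birth after conception on study day 25 in the last enrolled participant falls 24 + 266 − 151 = 139 days after the study period ends, about 17 August 2021.

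**Sensitivity**
- Conception 14 days before enrolment, missed by the test: 80/175 (46%) at 37 weeks and 101/175 (58%) at term.
- Delivery at 34 weeks (224 days): 73/175 (42%) for conception at enrolment and 97/175 (55%) for conception on day 25.
- So the share is above half for every 37-week or term birth conceived on study. It drops below half only when a very early conception or a preterm delivery brings the birth forward.

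**Do other rules fill the gap?**
- Scheduled contact: the staff schedule ends at day 40 (section 13, Table 2), and serious adverse events are monitored for 60 days (section 14.1.2). Both end well before 245 days.
- Section 14.3 records adverse events up to the participant's departure from the study and follows those to resolution. An uncomplicated pregnancy is not an adverse event, so this rule does not reach it.
- Section 14.1.2 counts a congenital anomaly as serious and follows a serious event that is still ongoing at exit. An anomaly first seen at a birth months later was not ongoing at exit.
- The closing cross-reference in 14.4 leads to no longer follow-up rule.

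**The case against.** The best defence is that the first sentence of 14.4 is an unconditional duty on the sponsor, and that the second only says how long follow-up runs at the study centre. On that reading, closing a centre does not release the sponsor. This is a possible reading, so a reader who infers that birth data cannot be collected goes too far: nothing in the text forbids later contact, and some births from early enrolments would fall before 31 March 2021. But the protocol names no procedure, contact or time point for the sponsor after close-out, and 11.1 gives the close-out limit without the sponsor's commitment beside it. The conflict therefore needs resolving in the text.

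The close-out date is also inferred, since no section equates it with the end of the study period. That stands, and the percentages depend on it. A close-out at the level of the home, for instance after its day 60 visit, would widen the gap to every 37-week or term birth conceived on study, but the protocol does not say that a home closes then.

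Other stronger readings are not supported:
- A reader might count 37 to 40 weeks as 259 to 280 days from conception and obtain 108 to 129 of 175 days (62% to 74%) for conception at enrolment. Those weeks are conventionally counted from the last menstrual period; from conception they are about 245 to 266 days.
- A reader might infer that most participants are affected. A share of enrolment days is not a count of pregnancies, and the entry test, the contraception requirement and the short course make pregnancies few.
- A reader might call this the only serious risk named, or the only safety follow-up able to detect it. Section 10.1.7 also discusses mutagenesis and gastrointestinal lesions, and complications of pregnancy do fall under the adverse event rules. Nor could a handful of pregnancies establish or exclude teratogenicity.

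**Conclusion.** The point holds as an internal conflict in sections 14.4 and 11.1: the required duration of follow-up does not secure the data that 14.4 promises. With close-out on 31 March 2021 and 245 to 266 days from conception to birth, the birth falls after close-out for 54% to 66% of enrolment days if conception is at enrolment, and for 67% to 79% if it is on study day 25. Both the close-out date and the time to birth are assumptions. The adverse event rules narrow the gap but leave out the uncomplicated pregnancy and the anomaly first found at birth after exit.

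The importance is low. Very few pregnancies are likely, and the efficacy analyses are unaffected. It is worth correcting because the protocol itself states the potential teratogenicity and gives the drug to working-age staff.

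**What to change.** In sections 11.1 and 14.4, replace the close-out end point for pregnancy data collection with: *until the outcome of the pregnancy and the status of the child are known, including after study close-out*. This concerns data collection only and changes nothing in treatment.

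The cost is a protocol amendment with REB approval (sections 16.3 and 17.1.1), a check that consent covers contact after close-out and the recording of the child's status, and telephone contact with very few participants. The consent forms are not in the text at hand, so whether they already cover this could not be checked.
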